9.6 Efficacy Subgroup Analyses

Subgroup analysis based on age group (< 40 years, $\geq 40 - < 65$ years, ≥ 65 years), sex (male, female), BMI classification (underweight or normal [< 25] and overweight or obese [≥ 25]), baseline monthly migraine days (< 8 days, and ≥ 8 days), prior exposure (yes/no) to a migraine prevention medication with proven efficacy, number of migraine prevention medication failures with proven efficacy (category details below), migraine diagnosis history (migraine with aura, migraine without aura, and migraine both with and without aura), and prior exposure to calcitonin gene-related peptide (CGRP) antagonists (yes/no) will be performed for the following efficacy endpoints

- Change from baseline in mean monthly migraine days across the 12-week double-blind treatment period.
- Change from baseline in mean monthly headache days across the 12-week double-blind treatment period.
- Change from baseline in mean monthly acute medications use days across the 12-week double-blind treatment period.
- At least a 50% reduction in 3-month average of monthly migraine days.

The between-group treatment effect (with a 95% CI) for each atogepant dose vs placebo for the specified efficacy endpoints will be estimated within each category of the subgroup. If models do not converge, descriptive statistics for subgroups will be provided.

Subgroup by number of migraine prevention medication failures with proven efficacy are specified as the following categories:

- Failed 0 medication,
- Failed 1 or more medication(s) with the same mechanism of action,
- Failed 2 or more medications with different mechanisms of action,
- Never used.

10.0 Safety Analyses

10.1 General Considerations

For the purposes of safety analysis, the start of the active treatment extension period is marked by the date of the first dose of study medication received in the active treatment extension period (Visit 6, Visit 7, or Visit 8).

Safety data will be summarized for the Safety Populations 1 and 2. Safety summaries will be presented by treatment groups. For the safety analysis, subjects are assigned to a treatment group based on the treatment actually received, regardless of the treatment randomized.

The safety parameters will include AEs, clinical laboratory evaluations, vital sign measurements, ECG parameters, and the C-SSRS. For each of the clinical laboratory, vital sign, and ECG parameters, the last non-missing safety assessment before the first dose of treatment will be used as the baseline for all analyses of that safety parameter.

Continuous variables will be summarized by the number of subjects, and mean, SD, median, Q1, Q3, minimum, and maximum values. Categorical variables will be summarized by number and percentage of subjects.

Descriptive statistics for safety endpoints will be provided by treatment period (double-blind treatment period or active treatment extension period), separately. For selected safety endpoints, analyses will be provided across both treatment periods to show the trend over time.

10.2 Adverse Events

Adverse events (AEs) will be summarized and presented using primary MedDRA System Organ Classes (SOCs) and preferred terms (PTs) according to the version of the MedDRA coding dictionary used for the study at the time of database lock. The actual version of the MedDRA coding dictionary used will be noted in the AE tables and in the clinical study report. Specific adverse events will be counted once for each subject for calculating percentages, unless stated otherwise. In addition, if the same adverse event occurs multiple times within a subject, the highest severity and level of relationship to investigational product will be reported.

10.2.1 Treatment-Emergent Adverse Events

Treatment-emergent adverse events (TEAEs) are defined as any AE with an onset after the first dose of study treatment and no more than 30 days after the last dose of study treatment. Events where the onset date is the same as the study treatment start date are assumed to be treatment-emergent, unless the study treatment start time and the AE start time are collected and the AE start time is prior to the study treatment start time. If an incomplete onset date is collected for an AE, then the AE will be assumed to be treatment-emergent unless there is evidence that confirms that the AE was not treatment-emergent (e.g., the AE end date was prior to the date of the first dose of study treatment).

An AE is considered a TEAE for the double-blind treatment period if the onset date is after the first dose of study treatment and no more than 1) 30 days after the last dose of double-blind study treatment or 2) the day before the date of the first dose of the active treatment extension study medication, whichever is earlier. An AE is considered a TEAE for the active treatment extension period if the AE begin on or after the date of the first

dose of the active treatment extension period study medication and no more than 30 days after the last dose of active treatment extension study treatment. TEAEs that start after the date of last dose of study treatment for each treatment period will be considered as newly emergent for the corresponding treatment period.

All treatment-emergent AEs will be summarized overall, as well as by primary MedDRA SOC and Preferred Term for the double-blind treatment period and active treatment extension period based on the Safety Population 1 and Safety Population 2, respectively. The SOC's will be presented in alphabetical order, and the PTs will be presented in alphabetical order within each SOC.

The number and percentage of subjects experiencing newly emergent treatment-emergent AEs will be summarized by period. The analysis population for the double-blind treatment period and active treatment extension period will be subjects in Safety Population 1 who entered the safety follow-up period without study treatment in the active treatment extension period and subjects who entered the safety follow-up period in Safety Population 2, respectively.

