APPENDIX H. ACTIVITY SCHEDULE

The following tables show the required activities. The individual activities are described in detail in the **Operations Manual** ([Appendix J](#)).

Table 3. Schedule of Activities

Activity	Screening period (4 weeks)	Double Blind Treatment Period (12 weeks)				Active Treatment Extension Period (dose blinded, 12 weeks)			Follow up Period (30 days)
	Visit 1/ Screening/ Baseline	Visit 2	Visit 3	Visit 4	Visit 5/ ET DB	Visit 6	Visit 7	Visit 8/ ET EX	Visit 9/EOS
	Week 4 (Day 35 to Day 28)	Day 1	Week 4 (Day 28) ± 3 days	Week 8 (Day 56) ± 3 days	Week 12 (Day 84) + 3 days	Week 16 (Day 112) ± 3 days	Week 20 (Day 140) ± 3 days	Week 24 (Day 168) + 3 days	Week 28 (Day 198/ 30 days after the last dose of study drug) + 3 days
INTERVIEWS & QUESTIONNAIRES									
Informed consent	✓								
Informed consent for biomarker research (optional)	✓								
Eligibility criteria	✓	✓							
Demographics	✓								
Medical history	✓								
Migraine headache history	✓								
Review prior medications including all migraine prophylactic medication use	✓								
Menstrual cycle assessment	✓	✓	✓	✓	✓	✓	✓	✓	✓
Adverse events	✓	✓	✓	✓	✓	✓	✓	✓	✓
Concomitant medications/concurrent procedures	✓	✓	✓	✓	✓	✓	✓	✓	✓
Provide eDiary, instructions and training	✓								
eDiary data collection	✓	✓	✓	✓	✓				
Collect eDiary device		✓			✓				
Review of eDiary data and compliance		✓	✓	✓	✓				

Activity	Screening period (4 weeks)	Double Blind Treatment Period (12 weeks)				Active Treatment Extension Period (dose blinded, 12 weeks)			Follow up Period (30 days)
	Visit 1/ Screening/ Baseline	Visit 2	Visit 3	Visit 4	Visit 5/ ET DB	Visit 6	Visit 7	Visit 8/ ET EX	Visit 9/EOS
	Week 4 (Day 35 to Day 28)	Day 1	Week 4 (Day 28) ± 3 days	Week 8 (Day 56) ± 3 days	Week 12 (Day 84) + 3 days	Week 16 (Day 112) ± 3 days	Week 20 (Day 140) ± 3 days	Week 24 (Day 168) + 3 days	Week 28 (Day 198/ 30 days after the last dose of study drug) + 3 days
C SSRS (eTablet)	✓	✓	✓	✓	✓	✓	✓	✓	✓
ASC 12 (eTablet)	✓								
HIT 6 (eTablet)		✓	✓	✓	✓				
PGIC (eTablet)					✓				
PGI S (eTablet)		✓	✓	✓	✓				
WPAI:MIGRAINE (eTablet)		✓	✓	✓	✓				
PSSM (eTablet)			✓	✓	✓				
EQ 5D 5L (eDiary)	✓	✓	✓	✓	✓				
MIDAS (eTablet)		✓			✓				
MSQ v2.1 (eTablet)		✓	✓	✓	✓				
PROMIS PI (eTablet)		✓	✓	✓	✓				
PHQ 9 (eTablet)		✓			✓				
 LOCAL LABS & EXAMS									
Physical examination	✓				✓			✓	✓
Height (Visit 1 only) and weight	✓	✓	✓	✓	✓	✓	✓	✓	✓
Vital sign measurements	✓	✓	✓	✓	✓	✓	✓	✓	✓
12 lead ECG	✓				✓			✓	

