6.0 Study Treatment Duration and Compliance

For the Safety Populations, duration of treatment will be summarized for each treatment group. The treatment groups for active treatment extension period will also include three additional columns for the lead-in placebo re-randomized group. Duration of treatment is defined for each subject as last dose date minus first dose date + 1. Duration of treatment for a treatment period is defined for each subject as last dose date minus first dose date + 1. Duration of treatment will be summarized separately for each period (double-blind treatment period and active treatment extension period) using the number of subjects treated, mean, standard deviation, median, Q1, Q3, minimum and maximum. In addition, the number and percentage of subjects in each treatment duration interval for double-blind treatment period and active treatment extension period (≥ 1 day, ≥ 7 days, ≥ 14 days, ≥ 21 days, ≥ 28 days, ≥ 35 days, ≥ 42 days, ≥ 49 days, ≥ 56 days, ≥ 63 days, ≥ 70 days, ≥ 77 days, ≥ 84 days) and overall (≥ 1 day, ≥ 7 days, ≥ 14 days, ≥ 21 days, ≥ 28 days, ≥ 35 days, ≥ 42 days, ≥ 49 days, ≥ 56 days, ≥ 63 days, ≥ 70 days, ≥ 77 days, ≥ 84 days, ≥ 91 days, ≥ 98 days, ≥ 105 days, ≥ 112 days, ≥ 119 days, ≥ 126 days, ≥ 133 days, ≥ 140 days, ≥ 147 days, ≥ 154 days, ≥ 161 days, ≥ 168 days) will be summarized by treatment group.

Subject-years, defined as exposure to the study treatment in years, will be summarized by treatment group for the Safety Populations.

Treatment compliance for a specified period is defined as the total number of study medications actually taken by a subject during that period divided by the number of study medications that were expected to be taken during the same period multiplied by 100. The total number of actual capsules taken during a specific period will be calculated from the study medication record.

Descriptive statistics for study medication dosing compliance together with the compliance categories ($< 80\%$, $80\% - 120\%$, $> 120\%$) will be summarized by study treatment group for each period between 2 consecutive visits, for the period from the first dose of the double-blind study interventions actually taken to the last dose of double-blind

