10.2.3 Treatment-Emergent Adverse Events by SOC and/or PT

Treatment-emergent adverse events will be summarized by treatment group, for each treatment period and overall, by SOC and PT; by maximum relationship to study treatment as assessed by the investigator (e.g., reasonable possibility or no reasonable possibility) and SOC and PT; by maximum severity and SOC and PT; and by subject number and SOC and PT. Specific adverse events will be counted once for each subject for calculating percentages, unless stated otherwise. In addition, if the same adverse event occurs multiple times within a subject, the highest severity and level of relationship to investigational product will be reported.

The incidence of common ($\geq 2\%$ of subjects in any treatment group) TEAEs will be summarized by preferred term, and treatment group. A similar 5% table will be provided as well.

10.2.4 Deaths, Serious Adverse Events, and Adverse Events Leading to Study Treatment Discontinuation

Treatment-emergent serious adverse events (TESAEs) and TEAEs leading to premature discontinuation of study treatment will be summarized by SOC and PT for each treatment period. TESAEs will also be summarized by SOC and PT overall.

For TEAEs leading to premature discontinuation of study treatment, summaries by SOC and PT will be provided as follows:

- TEAEs with start date and treatment discontinuation date in the double-blind period
- TEAEs with start date and treatment discontinuation date in the extension period
- TEAEs leading to treatment discontinuation during the extension period, i.e., the treatment discontinuation date occurred in the extension period regardless of whether the TEAE started in the double-blind period or the extension period.

Tabular listings will be provided for all deaths, all SAEs and TEAEs leading to premature discontinuation of study treatment.

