10.3 Analysis of Laboratory Data

The clinical laboratory tests defined in the protocol operations manual (e.g., hematology, clinical chemistry, and urinalysis) will be summarized.

Each laboratory variable will be summarized by treatment group for all time points (starting with Baseline) with the number of non-missing observations, mean and standard deviation, median, Q1, Q3, minimum and maximum. Mean change from baseline to each applicable post-baseline visit will be summarized for selected laboratory variables, with the number of observations, baseline mean, and visit mean. In addition, descriptive statistics for values and changes from the baseline values in conventional units at each assessment time point will be presented for selected clinical laboratory parameters listed in [Appendix D](#). A description of reporting the lab values in conventional units in patient narratives (along with the standard reporting in SI units) is presented at the end of [Appendix D](#).

Laboratory abnormalities will be evaluated based on Potentially Clinically Significant (PCS) criteria ([Appendix C](#), Table C-1). For each laboratory PCS criterion, the number

and percentage of subjects who have a laboratory value meeting the criteria will be summarized by treatment group. Listings will be provided to summarize subject-level laboratory data for subjects meeting PCS criteria.

The number and percentage of subjects meeting each of the criteria for postbaseline hepatic laboratory abnormalities listed in [Appendix C](#), Table C-2 will be summarized. The percentages will be calculated relative to the number of subjects with at least 1 available postbaseline assessment. The numerator will be the total number of subjects having at least 1 postbaseline value that meets the specific category during the study. A supportive listing will also be provided.

The number and percentage of subjects with an adjudicated case (i.e., $ALT \geq 3 \times ULN$ and/or $AST \geq 3 \times ULN$) will be summarized by treatment group and by relationship of ALT or AST elevation to study medication. The percentages will be calculated relative to the number of subjects with at least 1 adjudicated case. The numerator will be the number of subjects with at least 1 adjudicated case in the specific category of relationship. If a subject has more than 1 adjudicated case, he or she will be counted in the most relevant category of relationship.

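### Crude AE percentages are not like for like between periods, or in overall tables between continuing-atogepant and placebo-origin subjects, because counting windows differ (about 84, 114 and 198 days)

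*SAP*

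**What the plan says.** SAP 10.2.1 gives each period its own window. The double-blind window ends at the sooner of two dates: 30 days after the last double-blind dose, or "the day before the date of the first dose of the active treatment extension study medication, whichever is earlier". The extension window starts with the first extension dose and includes onsets "no more than 30 days after the last dose of active treatment extension study treatment". Events after a period's last dose are also shown in a separate newly emergent table.

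SAP 10.2.3 states: "Treatment-emergent adverse events will be summarized by treatment group, for each treatment period and overall". Its measure is the number and percentage of subjects, each counted once per event. SAP 6.0 says "Subject-years, defined as exposure to the study treatment in years, will be summarized by treatment group", but no AE table uses that quantity as a denominator, and the duration defined there counts dosing days only.

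SAP 4.0 fixes a subject's actual treatment by the first dose received. SAP 6.0 adds columns for re-randomized placebo subjects, but only in the duration summary.

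SAP 10.1 promises safety statistics by period and adds, for selected endpoints that it does not name, that "analyses will be provided across both treatment periods to show the trend over time". For hepatic categories, SAP 10.3 counts subjects with "at least 1 postbaseline value that meets the specific category during the study".

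**The concern.** Nearly all subjects are expected to roll over, so the double-blind table counts mostly on-treatment days while the extension table counts the same number of on-treatment days plus a month off treatment. A crude percentage grows with the length of the window. A reader who sets the two tables side by side cannot tell a longer window from accumulating toxicity, and a falling hazard could be hidden.

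The overall tables raise a second problem. The SAP does not say how placebo-origin subjects are shown there. If SAP 4.0 is applied literally, they stay under placebo, and that column includes their events on atogepant. If their column is cut at crossover, about 84 placebo days sit beside about 198 days for continuing subjects. Crude percentages mislead under either reading. The extension supplies this trial's longer-exposure safety data, and Protocol 2.1 says the study is meant to support registration in Japan.

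**Working it through.** **Inputs.** From Protocol Appendix H, Table 3: the double-blind period ends at Visit 5 (Day 84), extension dosing ends at Visit 8 (Day 168), and Visit 9 is on Day 198, described as "30 days after the last dose of study drug". The window rules come from SAP 10.2.1. The planned 5.4% double-blind dropout comes from SAP 2.4. Visit windows of 3 days are ignored, and the first extension dose is taken as Day 85.

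**The schedule's own figure.** 168 + 30 = 198, which agrees with Visit 9.

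**Windows.**
- Double-blind, subject who rolls over: Day 1 to 84 = 84 days, no tail.
- Extension: Day 85 to 198 = 198 − 85 + 1 = 114 days (84 dosing + 30 off treatment). Ratio 114/84 = 1.36.
- Overall, subject kept on atogepant: Day 1 to 198 = 198 days. Ratio to 84 placebo days: 198/84 = 2.36.

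**Allowing for dropouts.** Subjects who stop in the double-blind period and never start the extension do get the tail. Assume 5.4% stop in each period, evenly over time, with a mean of 42.5 + 30 = 72.5 days. The mean windows are 0.946 × 84 + 0.054 × 72.5 = 83.4 days and 0.946 × 114 + 0.054 × 72.5 = 111.8 days, ratio 1.34.

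**Effect on a crude percentage.** Assume a constant on-drug hazard, and let f be the off-drug hazard as a fraction of it. If p is the 84-day percentage, the extension percentage is 1 − (1 − p)^((84 + 30f)/84). For p = 10%:
- f = 0: 10.0%
- f = 0.5: 1 − 0.9^(99/84) = 11.7%
- f = 1: 1 − 0.9^(114/84) = 13.3%

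At f = 1, 2% becomes 2.7%, 5% becomes 6.7% and 30% becomes 38.4%. Over the overall window the exponent is (168 + 30f)/84, so 10% becomes 19.0% at f = 0 and 22.0% at f = 1. Conversely, a hazard lower by 1 − 84/114 = 26% throughout the extension window would give the same percentage as the double-blind period.

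**What an exposure-adjusted rate does.** With p = 10%, the hazard is −ln(0.9)/84 = 0.001254 per day, or 0.001254 × 365.25 × 100 = 45.8 per 100 subject-years. With the tail in the time at risk, both periods show 45.8. If tail events are divided by dosing days only, the extension shows 45.8 × 114/84 = 62.2, and an overall table is inflated by 198/168 = 1.18.

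**The newly emergent table.** Its double-blind version covers only subjects who entered follow-up without extension treatment: about 0.054 × 130 = 7 per arm. Its extension version starts from about 123 in each continuing arm. It shows the tail but does not take tail events out of the main tables.

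**The date that divides the windows.** SAP 10.1 places the first extension dose at Visit 6, 7 or 8, whereas Table 3 dispenses drug at Visit 5. If Visit 6 (Day 112) were taken as the start, the double-blind window would close on Day 111 (the sooner of 84 + 30 = 114 and 112 − 1 = 111). The windows would then be 111 and 198 − 112 + 1 = 87 days.

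**The case against.** The SAP plans no formal comparison of AEs between periods. SAP 10.1 reports the periods separately and on different safety populations. The comparisons that matter most, atogepant against placebo in the double-blind period and dose against dose in the extension, apply one rule to every arm. The newly emergent table, the duration summary and the subject-years let a careful reader see the difference, and a cumulative percentage is expected to exceed a 12-week one. All of this stands and limits the point to descriptive reporting. It does not make the crude percentages comparable, and it does not settle where placebo-origin subjects appear in the overall tables.

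A reader might go further and infer that AE rates must rise with time on drug by construction. The documents do not support that. The extra 30 days are off treatment, the quantity affected is a percentage and not a rate, and there is no rise if the off-drug hazard is zero. Entry limited to completers, or AEs that start early, could push the other way. Nor is the 84-day window universal, since subjects who never start the extension get the tail. A reader might also take the trend-over-time sentence in SAP 10.1 to cover AEs, but it names no endpoint.

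The laboratory side is weaker. Table 3 schedules three post-baseline draws in the double-blind period (Visits 3 to 5) and four afterwards (Visits 6 to 9), the last of them off treatment. SAP 10.1 already calls for reporting by period, so 10.3 needs only a clarification.

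**Conclusion.** The point holds as one about reporting. For subjects who roll over, the windows are about 84 and 114 days, a ratio of 1.36 (1.34 with the assumed dropout). Overall tables reach about 198 days on continuing atogepant against about 84 on placebo. For an AE at 10% in the double-blind period, the extension figure lies between 10.0% and 13.3%, and the overall figure is at most 22.0%. These percentages rest on an assumed constant on-drug hazard and on off-drug hazards between 0 and 1 times that value; the documents give neither. The day counts follow directly from the schedule and SAP 10.2.1, provided the first extension dose follows Visit 5.

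The randomized safety comparison with placebo in the double-blind period and the dose comparisons within the extension are unaffected. This is a worthwhile, inexpensive improvement and not a flaw in the trial's main safety evidence.

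**What to change.** - **SAP 10.2.2 and 10.2.3:** keep the 30-day definition and the crude percentages. Add exposure-adjusted incidence rates to the by-period and overall tables: subjects with a first event, and events, per 100 subject-years.
- **Denominator:** use the actual time at risk for treatment-emergent AEs. Include tail days wherever tail events are counted, and censor at the first event for first-event rates. Do not use the dosing-only subject-years of SAP 6.0.
- **Overall tables:** show the placebo time and the atogepant time of placebo-origin subjects separately, so that events on atogepant are not counted under placebo.
- **SAP 10.3:** tabulate the hepatic categories by period, as SAP 10.1 states.
- **SAP 10.1 and Protocol Appendix H, Table 3:** reconcile the visit that marks the extension start with the visit at which drug is dispensed.

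The cost is a derived time-at-risk variable and some extra table columns, from data already collected. Cutting both windows at the last dose would also equalize them (84 against 84 days), but it would remove post-dose events from the main tables, against the SAP's own 30-day definition.
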